9.5.1.1 Assumptions used for the sample size and power calculations

To estimate the number of anifrolumab exposed SLE pregnancies and the expected number of primary study outcome events in data sources that would be eligible for the analysis in this study, the following assumptions were used:

- **A prevalence of 7% for MCM outcome.** Prevalence of MCM in pregnancies in women with moderate-to-severe SLE was estimated based on a literature search. Among moderate/severe SLE patients exposed to belimumab, birth defect prevalence estimates of 5.6% to 21.7% were observed in post hoc summary of clinical studies and a prospective

pregnancy registry, respectively (86) A prevalence of 6.4% of congenital malformations was observed in renal SLE pregnancies (51) These proxy estimates of MCM in moderate-to-severe SLE align with the observed population based prevalence estimates ranging from 7.4% to 13.6% (114) among women diagnosed with SLE (117).

- **A prevalence of 20% for the composite of select pregnancy loss outcomes (composite of spontaneous abortion and stillbirth).** Prevalence of the composite outcome of select pregnancy loss (spontaneous abortion and stillbirth) in moderate-to-severe SLE pregnancies ranged from 15.3% to 30% (51, 81, 86). For the individual outcomes, the prevalence estimates ranged from 1.8% to 3.7% for stillbirths (51, 103, 120), and the prevalence estimate was 16% (12.1% to 19.9%) for spontaneous abortions (103). Based on the intended objective to evaluate embryo-foetal loss, a composite outcome of spontaneous abortion and stillbirth has been used.
- **Proportion of SLE pregnancies occurring in women with moderate-to-severe disease of 50%.** There is limited information on the proportion of SLE pregnancies that occur in women with moderate-to-severe disease. The proportion of moderate-to-severe disease at the time of diagnosis among the general SLE population is estimated to be 50% (66, 80). Literature regarding medication patterns for SLE pregnant women suggests that 40-45% use immunosuppressors and/or biologics, which may be a proxy indicator of moderate/severe disease (12, 67). Thus, in this study, an assumption of 50% was used.

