The summary of the estimated annual number of pregnancies in women with moderate-to-severe SLE eligible for the primary outcome analysis are shown in [Table 9](#) for each data source and anifrolumab exposure proportion scenarios. The MCM analysis will only consider the pregnancies where anifrolumab exposure occurs during the first trimester of pregnancy, and it is assumed that 80% of all anifrolumab exposed pregnancies have exposure to anifrolumab within the first trimester of pregnancy. Based on these estimates and assuming that 5% of pregnancies in moderate to severe SLE patients are exposed to anifrolumab, the total number of anifrolumab exposed patients by the end of the study time period (September 2030 in USA, September 2028 in other study countries) is estimated to be 249 (82 [Carelon Research], 81 [DAPI], 5 [Denmark], 3 [Finland], 73 [France] and 5 [RHEKISS]) patients ([Table 10](#)) for the select pregnancy loss outcome

and 175 (51 [Carelon Research], 56 [DAPI], 4 [Denmark], 3 [Finland], 58 [France] and 3 [RHEKISS]) for the MCM outcome.

Under the assumption of 10% of pregnancies in moderate to severe SLE patients exposed to anifrolumab, the estimated number at the end of the study period is 497 (163 [Carelon Research], 162 [DAPI], 11 [Denmark], 7 [Finland], 145 [France] and 9 [RHEKISS] patients (Table 11) for the select pregnancy loss outcome and 353 (102 [Carelon Research], 114 [DAPI], 8 [Denmark], 6 [Finland], 116 [France] and 7 [RHEKISS]) for the MCM outcome.

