9.7 Data Analysis

All data analysis will be performed separately for each data source on the study population as defined in Section 9.2.2. The study population selection process will be reported using a STROBE

(STrengthening the Reporting of OBservational studies in Epidemiology) diagram that shows cohort and sub-population exclusions step by step, as defined in Section 9.2.2.

All study results will be presented separately for each data source in the study reports, as appropriate when data become available. The full study reports for all data sources, including all descriptive, comparative, exploratory, and sensitivity analyses, as well as the meta-analysis results will be provided in the final report. The study reporting is described in detail in Section 6.

A full description of the analytical approach will be developed and described in the SAP. Also details on data derivations, category definitions, analyses, and presentation of the study results will be provided in SAP. The SAP will be finalised prior to the conduct of the study analyses.

In this study, the missing data will be reported as part of descriptive analysis (see Section 9.7.1). Methods commonly used in non-interventional studies for handling missing data, such as imputation, complete case analysis or indicator for missing values, will be considered (35). The SAP will describe the full details on handling missing data that will include the methods for identifying where missing data methods should be applied, the techniques for identifying the type of missing information and the appropriate imputation methods to be used, if any.

The small number masking rules define the lower limit for the number of units that can be reported in a table. The small number masking rules vary by data sources. For example, Denmark and Finland have a limit of 5, USA (Carelon Research) has a limit of 10 and France has a limit of 11. The small number masking rules of the data sources will be considered when presenting the study results for descriptive and comparative analysis. If the small number masking rules apply, only the comparative analysis results for the relevant study outcome (and no descriptive analysis results for the relevant study outcome) will be provided to avoid inadvertent unmasking of small numbers.

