In the descriptive analysis, the total number of patients at risk and the number of events for each study outcome in the study sub-cohorts (exposed to anifrolumab and unexposed to anifrolumab as defined in Section 9.2.2) will be tabulated before and after application of PS adjustment, if suitable for the data. The measures of study outcomes will be estimated before and after application of PS adjustment (if suitable for the data) to obtain crude and adjusted estimates, respectively. The measures of study outcomes, with associated 95% CIs, will be estimated for the study sub-cohorts exposed to anifrolumab and unexposed to anifrolumab as defined in Section 9.2.2. In this study, cumulative incidence (i.e. incidence proportion) by exposure status to anifrolumab during pregnancy will be assessed for the following study outcomes: MCM (objective 1 & 15), select pregnancy loss outcomes (composite of spontaneous abortion and stillbirth) (objective 3 & 13), mCM (objective 6), adverse pregnancy outcomes (objective 8), adverse birth outcomes (objective 10), and adverse outcome related to infant growth up to one year of age (objective 12).

Additionally, the description of the time from birth to MCM ascertainment will be conducted in live and non-live offspring from women who had moderate/severe SLE and were exposed or unexposed to anifrolumab during the first trimester of pregnancy. The time to MCM ascertainment will be calculated from birth and up to 1 year after birth. The time to MCM ascertainment will be estimated both before and after application of PS adjustment (if suitable for the data) to obtain crude and adjusted estimates, respectively. Kaplan-Meier curves (and their 95% CIs) will be used for characterising the time from birth to MCM ascertainment. Together with the Kaplan-Meier curves, the number of patients at risk at appropriate time intervals (e.g., 7 days or as seen appropriate for the study), and the median (with 95% CI) for the time from birth to MCM ascertainment will be reported.

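### The planned Kaplan-Meier median time from birth to MCM will not be reached at the protocol's 7% risk, and birth is not a usable time origin for the non-live offspring included

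*Protocol*

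**What the plan says.** Section 9.7.1 (Descriptive analysis) fixes four elements of this output:

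- **Population:** "the description of the time from birth to MCM ascertainment will be conducted in live and non-live offspring".
- **Time origin and window:** "The time to MCM ascertainment will be calculated from birth and up to 1 year after birth".
- **Estimator:** "Kaplan-Meier curves (and their 95% CIs) will be used for characterising the time from birth to MCM ascertainment".
- **Summary:** numbers at risk, and "the median (with 95% CI) for the time from birth to MCM ascertainment will be reported".

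The estimates are to be given by exposure group, before and after propensity-score adjustment. Section 9.7.2 repeats the plots, but not the median, under primary Objective 1. Section 9.7 says "All data analysis will be performed separately for each data source", so each source produces its own curve and median.

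Section 9.5.1.1 assumes "A prevalence of 7% for MCM outcome". In the literature it cites for women exposed to belimumab, "birth defect prevalence estimates of 5.6% to 21.7% were observed".

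Section 9.3.2 gives a window from birth to 1 year only to live births. For spontaneous abortion and stillbirth, MCM is ascertained at the end of pregnancy. For elective termination, it is ascertained at the termination. Table 5 nevertheless places all three kinds of non-live outcome in the MCM cohort.

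**The concern.** A Kaplan-Meier median is the time at which the estimated event-free proportion first drops to one half. Here the curve covers all offspring, most of whom never have an MCM, and follow-up stops at 1 year. The proportion with an event is far below one half, so the named summary cannot be produced.

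The second problem is the time origin. Part of the stated population was never born alive and has no follow-up after birth. The protocol does not say whether these offspring enter as events at day 0, are censored at day 0 or are left out, and the three choices give different curves.

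What is at stake is one descriptive output. As written, its headline number will read as not reached, and the curve will mix detection after birth with findings made at pregnancy loss.

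**Working it through.** **Inputs.** MCM risk 7% and highest cited prevalence 21.7% (Section 9.5.1.1). Exposed offspring at 10% uptake and a 2032 report: "353 (102 [Carelon Research], 114 [DAPI], 8 [Denmark], 6 [Finland], 116 [France] and 7 [RHEKISS]) for the MCM outcome" (Section 9.5.1.2). Non-live share of SLE pregnancies 20% (Section 9.5.1.2). Live births linkable: 73% in Carelon Research and 85% in DAPI (Section 9.5.1.2).

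**Step 1: reproduce the plan's own figures.** Expected events = n × 0.07:

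- Carelon Research: 102 × 0.07 = 7.1
- DAPI: 114 × 0.07 = 8.0
- France: 116 × 0.07 = 8.1

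Table 11 prints 7, 7 and 8. The chance of at least one event, 1 − 0.93^n, is above 99% in these three sources. It is 44%, 35% and 40% for n = 8, 6 and 7, as in Table 11.

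**Step 2: where the curve ends.** Event-free proportion at 1 year = 1 − risk.

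- At 7%: 1 − 0.07 = 0.93
- At 21.7%: 1 − 0.217 = 0.783

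Both are well above 0.50.

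**Step 3: chance of reaching the median without censoring.** At least half the offspring would need an MCM. The binomial tail probabilities are:

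| Source | n exposed | MCMs needed | Chance at 7% | Chance at 21.7% |
|---|---|---|---|---|
| Carelon Research | 102 | 51 | 1e-31 | 3e-10 |
| DAPI | 114 | 57 | 4e-35 | 3e-11 |
| France | 116 | 58 | 1e-35 | 2e-11 |
| Denmark | 8 | 4 | 0.1% | 7% |
| Finland | 6 | 3 | 0.6% | 12% |
| RHEKISS | 7 | 4 | 0.1% | 4% |

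Under the planning assumption of a true risk ratio of 1, the comparator group has the same 7% risk. At 1:2 or 1:3 matching it is two to three times larger, so the chance there is smaller still.

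**Step 4: does censoring rescue it?** Loss to follow-up could let the curve drop late, when few remain at risk. This was simulated at 7% risk, with event times uniform over the year (an assumption), 0 to 90% of offspring lost at random times, and 2,000 runs per setting. For n = 102 and n = 116 the median was reached in 0 runs at every loss rate. Up to 60% loss, the lower confidence limit for the median was not estimable in any run either. At 90% loss it became estimable in at most 0.85% of runs.

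**Step 5: how many offspring lack the time origin.** If 20% of pregnancies are non-live and only linked live births enter, the non-live share of the MCM cohort is 0.20 / (0.20 + 0.80 × linkage):

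- France: 0.20 / 1.00 = 20%
- DAPI: 0.20 / (0.20 + 0.80 × 0.85) = 0.20 / 0.88 = 23%
- Carelon Research: 0.20 / (0.20 + 0.80 × 0.73) = 0.20 / 0.784 = 26%

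This assumes that the 20% applies equally to exposed pregnancies. A fifth to a quarter of the stated population therefore has no time after a live birth.

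**The case against.** **The curves already answer the timing question.** A reader might infer that any difference in ascertainment timing between the groups would go unexamined. The documents do not support that. Section 9.7.1 plans curves with 95% CIs and numbers at risk for both groups, crude and adjusted. One minus the curve is the cumulative percentage ascertained at each age. Only the median is uninformative.

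**Objective 1 does not depend on it.** A reader might also infer that Objective 1 loses its main result. It does not: Section 9.7.2 makes the cumulative incidence with 95% CI the summary and adds the plots to it. The risk ratio in Objective 2 comes from log-binomial or modified Poisson regression. No power figure or decision uses the median.

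**The median is not impossible in every source at every risk.** At 21.7% the small sources could reach it by chance (4% to 12% in the table). The firm statement covers the three large sources across the cited range, and the small ones at 7%.

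**Non-live offspring can be given a time of zero.** Section 9.1 starts MCM ascertainment at the end of pregnancy, and a stillbirth has a delivery date. It would be too strong to say that no non-live offspring has any time value. What stands is that abortions and terminations have no birth date and that a day-0 value says nothing about detection after birth.

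**The SAP may settle it.** Section 9.7 defers details to the SAP. But the population, origin, estimator and median are already fixed here, and the text does not limit the median to offspring with an MCM.

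**Masking may suppress any replacement.** This stands. Section 9.7 sets limits of 5 in Denmark and Finland, 10 in Carelon Research and 11 in France. At 7% risk, the chance of fewer events than the limit is about 82% in Carelon Research (9 or fewer of 102) and 81% in France (10 or fewer of 116).

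**Conclusion.** The point holds as a minor defect in a descriptive analysis. The protocol commits to a median that will not be reached in Carelon Research, DAPI or France anywhere in its own cited prevalence range, and almost surely not in the small sources at 7%. It also measures time from birth in a population of which roughly 20% to 26% was not born alive.

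The conclusion rests on reading Section 9.7.1 as written, with all offspring in the Kaplan-Meier set, and on the protocol's risk, size, linkage and non-live assumptions. It does not touch the primary cumulative incidence, the risk ratio or the meta-analysis.

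**What to change.** Amend Section 9.7.1, and Objective 1 in Section 9.7.2 to match:

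- Restrict the time-to-ascertainment curve to live births.
- Report MCM in non-live offspring as a proportion, by exposure group.
- Replace the all-offspring median with the cumulative percentage ascertained, with 95% CI, at a few pre-set ages up to 1 year, read from the curve.
- Give a median age at ascertainment only among live-born infants with an MCM, labelled as such.
- State that all of this is reported only where the small-number masking rules in Section 9.7 allow.

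The cost is a wording change, with the same data and software. The downside is that, with about 7 to 8 exposed events per large source, these summaries may be masked in some sources. The ages should therefore be few and coarse.

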9. RESEARCH METHODS

9.1 Study design

The study will be performed using a non-interventional longitudinal population-based retrospective cohort design. It will be conducted using secondary data derived from multiple databases in Denmark, Finland, France, Germany, and USA. The unit of analysis is individual pregnancies in women with moderate/severe SLE. Therefore, each woman may contribute multiple occurrences of pregnancies to the study.

There are two primary outcomes of interest: **composite of MCM** and **select pregnancy loss outcomes**. The ascertainment period for MCM is from the end of the pregnancy until one year of age, while the ascertainment period for select pregnancy loss outcomes is from LMP2 until end of pregnancy. The study design schemas for these outcomes are provided in Figure 1 (MCM) and Figure 2 (select pregnancy loss outcomes) below.

The secondary outcomes of interest are mCM, adverse pregnancy outcomes, and adverse birth outcomes. The outcome ascertainment periods for these secondary outcomes are from birth until one year of age (mCM), from LMP2 until end of pregnancy (adverse pregnancy outcomes) and at birth (adverse birth outcomes). The study design schemas are presented in Figure 1 (mCM), Figure 2 (adverse pregnancy outcomes) and Figure 3 (adverse birth outcomes).

The exploratory outcomes of interest are adverse outcomes related to infant growth. The ascertainment period for this outcome is from birth until 1 year of age. The study design schema is presented in Figure 4. In addition to this exploratory outcome, analysis for the select pregnancy loss outcome (composite of spontaneous abortion and stillbirth) by specific trimester of anifrolumab exposure (details as provided in Section 9.3.1), and the risk of MCM by target body organ system classification according EUROCAT (41) will be conducted.

For congenital malformation (CM), birth and infant outcomes, the population of study will be limited to offspring for whom mother-offspring record linkage is available within each data source. However, for pregnancies that end in a spontaneous abortion, an elective termination of pregnancy or stillbirth where there is a diagnosis of MCM, mother-offspring linkage will not be required.

The exposure of interest is *in utero* exposure to anifrolumab (see Section 9.3.1) and/or *in utero* exposure to SLE SOC between last menstrual period + 2 weeks (LMP2) (derived from last menstrual period or, if missing, gestational age) and:

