9.5.1.3 Methods for estimating required sample size and expected power

The required sample size and expected power calculations were based on the assumptions described above and were carried out separately for each primary outcome (MCM and select pregnancy loss) at the meta-analysis level. Data sources that had at least a 90% probability of having at least 1 event in each exposure group (see [Table 10](#) and [Table 11](#)) were included in the meta-analysis.

The sample size and power calculations were performed using simulations under the assumption that the true RR is 1.0. For both sample size and power calculations, simulations were repeated 1,000 times to get 1,000 simulated 95% CIs for RRs.

The required sample size to achieve 80% power for a one-sided alpha-level of 2.5% at meta-analysis were performed using simulations as detailed below:

1. For a given overall sample size, a proportion of the overall population was assigned to each of the data sources likely to be included in the meta-analysis (proportions are presented in [Table 12](#)).
2. The number of primary outcome events in each exposure group were randomly drawn for each data source from a binomial distribution. In the binomial distribution, the number of trials was set equal to the estimated data source-level sample size and the probability of success was set to equal to the prevalence of the outcome in each exposure group, assuming that the true RR is 1 (no effect of exposure).
3. The estimated data source level log(RRs), their standard errors, and their 95% CIs were computed using a log-link Poisson regression (in place of log-binomial regression which tended to not converge) from the simulated number of events.
4. The data source level log(RRs) and their standard errors were entered in a fixed-effect meta-analysis model where pooled 95% CIs were computed. The inverse-variance method was used for the meta-analysis. The meta-analysis was run using the meta package in R ([97](#)).
5. The steps 2-4 were repeated for 1,000 times, and the proportion (which represents the achieved power) of the 1,000 simulated 95% CI upper bounds that were smaller than the target RR of 2.5 was computed.
6. The overall sample size was varied to range over positive integers for simulations, and the required sample size for this study was identified as the minimum overall sample size necessary to achieve 80% power (as defined in step 5).

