9.7.1 Methods

Propensity score methodology for confounding

Methods based on propensity score (PS) are frequently used in non-interventional studies to control for confounding when estimating treatment effects (6). PS methods allow for control of measured confounding in treatment effects when the measured confounders related with the treatment are correctly modelled in the PS (107). In non-interventional studies, the widely used methods that employ PS methods in adjusting for confounders include PS matching and PS weighting using inverse probability treatment weighting (IPTW). In this study, the average treatment effect in the treated (ATT) is the estimand of interest. To estimate ATT using PS matching, each patient within the study treatment is matched either to one (i.e. 1:1 matching) or more (i.e. 1:n matching) patients who have the same or a similar PS value (65). In PS matching, the patients in the study treatment cohort who do not have a close enough match in the comparator treatment cohort need to be excluded from the analysis (65). To estimate ATT using IPTW, each subject in the study treatment cohort has a weight of one and each subject in the comparator treatment cohort has a weight of the odds of receiving the study treatment i.e. $PS/(1-PS)$ (6). This

weighting approach is also known as standardised mortality ratio weighting, and it creates a pseudo-population of the comparator treatment cohort that has the same covariate distribution as the study treatment cohort (107). The PS weighting approach excludes patients from the original study population when there are non-overlapping PS values in the study cohorts (65). The PS weighting with IPTW is vulnerable to patients with extreme PS weights, but truncation methods will be used in this study if PS weighting is used and extreme PS weights are observed (19, 65).

In this study, PS matching will be considered as the preferable PS adjustment method. PS matching will be used if it does not significantly reduce the sample size, otherwise PS weighting will be used. In PS matching, if there are many more patients in the comparator treatment cohort than in the study treatment cohort, each patient in the anifrolumab exposed cohort may be matched to more than one patient (e.g., 1:2 or 1:3 matching) to increase statistical power.

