For the comparison of the study sub-cohorts exposed to anifrolumab and unexposed to anifrolumab within the study cohorts (as defined in Section 9.2.2), the association metrics of RRs will be estimated. The RRs will be estimated if there is at least one outcome event observed per exposure group. Both crude and adjusted RRs will be reported and estimated for each relevant study outcome. The crude and adjusted RRs will be estimated before and after PS adjustment, respectively. The adjusted RRs will be reported only if PS adjustment is suitable for the data. The statistical model to be used for the estimation of the crude and adjusted RRs will be the log-binomial regression or the robust, modified Poisson regression as seen appropriate for the study data (13, 18). If covariate balance is not achieved through PS adjustment, additional adjustment by using unbalanced covariates in the outcome regression model will be considered. Additionally, any other potential covariates (or risk factors) that are not included in the PS model but are hypothesised to be associated with the study outcomes may be used as covariates for the statistical models. Further details on the statistical models will be provided in the SAP.

Meta-analysis

In addition to data source level analyses, results will be combined in a meta-analysis. Meta-analysis will be performed only for the adjusted RR estimates of the primary study objectives (MCM and selected pregnancy loss outcomes). The meta-analysis will be performed using effect size estimates from all study countries for which the adjusted RR were estimated.

Prior to conducting the meta-analyses, heterogeneity across the study countries will be assessed using:

- Cochran's Q test (significance level: 0.1). Q is calculated as the weighted sum of squared differences between individual studies and the pooled value across studies.
- The I^2 statistic (0% to 40%: might not be important; 30% to 60%: may represent moderate heterogeneity; 50% to 90%: may represent substantial heterogeneity; 75% to 100%: considerable heterogeneity). I^2 is calculated as follows:

$$I^2 = \left(\frac{Q - df}{Q} \right) \times 100\%$$

where Q is Cochran's statistic and 'df' is its degrees of freedom. The I^2 is a statistic that estimates the percentage of variance in effects attributable to study heterogeneity rather than sampling error.

- The τ^2 statistic

Considerable heterogeneity would indicate that the study results should be interpreted as inconclusive.

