9.7.2 Primary objectives

The analysis for the primary study objectives will be conducted separately for each data source. In addition, meta-analysis will be performed to combine the adjusted RRs regarding the primary outcomes (i.e., MCM and select pregnancy loss outcomes) from the individual data sources where comparative analysis are performed as described in Section 9.7.1. The description of the analysis to be conducted for each primary study objective is provided in the following sections.

Objective 1

The analysis to describe and estimate the risk of MCM in live and non-live offspring from the mothers who had moderate/severe SLE and were exposed to anifrolumab during the first trimester of pregnancy or exposed to SOC and unexposed to anifrolumab during the first trimester of pregnancy (study objective 1) will be performed using the *MCM* cohort and its sub-cohorts as defined in Section 9.2.2). The crude and adjusted cumulative incidence (with corresponding 95% CI) of the MCM in live and non-live offspring from the mothers who had moderate/severe SLE and were exposed to anifrolumab during the first trimester of pregnancy or who were exposed to SOC and unexposed to anifrolumab during the first trimester of pregnancy will be estimated separately. The crude cumulative incidence (i.e., risk) will be calculated as the total number of live and non-live offspring with MCM divided by the total number of live and non-live offspring. The adjusted cumulative incidence (i.e., risk) will be estimated following PS adjustment, if suitable for the data. Additionally, the Kaplan-Meier plots will be generated both before and after application of PS adjustment to obtain crude and adjusted estimates for the time from birth to MCM ascertainment, respectively (as described in Section 9.7.1).

Objective 2

To estimate the relative risk of MCM in live and non-live offspring from the mothers who had moderate/severe SLE and were exposed to anifrolumab during the first trimester of pregnancy or exposed to SOC and unexposed to anifrolumab during the first trimester of pregnancy (study objective 2), the crude and adjusted RRs (with corresponding 95% CIs) will be estimated using the *MCM* cohort (as defined in Section 9.2.2). The crude RR and its 95% CI will be estimated using a regression model as specified in Section 9.7.1. The adjusted RR and its 95% CIs will be estimated by using the same regression model after applying an appropriate PS adjustment method

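### The relative-risk models carry no allowance for repeat pregnancies of one woman, and log-binomial regression is permitted after SMR weighting, where its usual variance is invalid

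*Protocol*

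**What the plan says.** Section 9.1 makes the pregnancy the unit of analysis and adds that "each woman may contribute multiple occurrences of pregnancies to the study". Table 7 lists previous spontaneous abortion as a risk factor for MCM, spontaneous abortion and stillbirth, and previous stillbirth as one for MCM and stillbirth. The protocol therefore expects outcomes to be related within a woman.

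Section 9.7.1 states that the model for "the crude and adjusted RRs will be the log-binomial regression or the robust, modified Poisson regression as seen appropriate for the study data". Section 9.7.2 has the adjusted RR "estimated by using the same regression model after applying an appropriate PS adjustment method". On propensity scores (PS), "PS matching will be considered as the preferable PS adjustment method"; weighting is used if matching loses too much of the sample. Under weighting each exposed pregnancy counts as one and "each subject in the comparator treatment cohort has a weight of the odds of receiving the study treatment", that is PS/(1−PS). Non-overlapping scores are excluded and extreme weights truncated.

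In the study-size simulation (Section 9.5.1.3), "The number of primary outcome events in each exposure group were randomly drawn for each data source from a binomial distribution".

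Nothing in the protocol mentions correlation within a woman, clustering on the mother or a variance for weighted data, and the limitations in Section 9.9 do not mention repeat pregnancies.

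**The concern.** Two features of the design affect the standard error of the RR.

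1. **Repeat pregnancies.** If outcomes are positively correlated within a woman and her pregnancies fall in the same exposure group, a record-by-record variance is too small. The robust variance in modified Poisson regression corrects the Poisson variance for a binary outcome. It allows for clusters only if the woman is named as the cluster.
2. **SMR weights.** The comparator weights add up to roughly the number exposed, however many comparators there are. A log-binomial fit with model-based variance reads that sum as a count of independent pregnancies.

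The standard errors set the confidence limits, the inverse-variance weights of the fixed-effect meta-analysis, and Q and I². Analyses are run separately by source, some of them by the data provider (Section 9.6). An open choice between two models could therefore pool standard errors built on different bases.

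**Working it through.** **Inputs from the protocol.** MCM risk 7%; RR margin 2.5; one-sided alpha 2.5%; true RR 1.0; 1:2 allocation. Exposed pregnancies in the three pooled sources are 102 + 114 + 116 = 332 at 10% uptake (Table 11) and 51 + 56 + 58 = 165 at 5% (Table 10).

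**Assumed, because the protocol gives no figures.** A fraction f of 10–50% of women contribute two pregnancies, both in the same arm; ICC 0.05–0.30.

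**Step 1: the plan's own figures.** I simulated independent binomial events per source, with variance 1/a + 1/b for log(RR), where a and b are the event counts, and inverse-variance pooling (100,000 replicates).

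| Setting | Stated power | Reproduced |
|---|---|---|
| MCM, 210 exposed, 1:2 | 80% | 80.5% |
| MCM, 183 exposed, 1:3 | 80% | 79.2% |
| Pregnancy loss, 72 exposed, 1:2 | 80% | 81.8% |
| Pregnancy loss, 61 exposed, 1:3 | 80% | 79.3% |
| MCM, 332 exposed, 1:2 / 1:3 | 96% / 98% | 96.1% / 98.2% |
| MCM, 165 exposed, 1:2 / 1:3 | 69% / 72% | 66.1% / 72.5% |

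The largest gap, at 165 exposed and 1:2, is about two Monte Carlo standard errors of the protocol's 1,000 runs. A binomial variance gives 68.8% there. The stated figures hold under independence.

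**Step 2: repeat pregnancies.** DEFF = 1 + (Σm²/Σm − 1) × ICC, where m is the number of pregnancies per woman and Σm²/Σm = (1 + 3f)/(1 + f).
- f = 0.1, ICC 0.05: 1 + (1.3/1.1 − 1) × 0.05 = 1.009.
- f = 0.5, ICC 0.30: 1 + (2.5/1.5 − 1) × 0.30 = 1.20.

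The width of the interval for log(RR) scales with √DEFF: 1.005 to 1.095. The MCM requirement becomes 210 × DEFF = 212 to 252.

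Closed-form power is Φ(ln 2.5/√(v × DEFF) − 1.96), with v = 1/(0.07n) + 1/(2 × 0.07n).
- n = 332: v = 0.0645; power 95.0%, falling to 94.8% (DEFF 1.009) and 90.9% (DEFF 1.20).
- n = 165: v = 0.1299; power 72.0%, falling to 71.6% and 64.1%.

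The closed form differs by a few points from the simulated level at 165 exposed, so read the change rather than the level. With beta-binomial outcomes, 332 exposed, a true RR of 2.5 and unclustered intervals, the simulated one-sided error was 2.2–3.7%, against 2.4% without clustering.

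**Step 3: SMR weighting with model-based log-binomial variance.** Uptake of 5% and 10% leaves 95/5 = 19 and 90/10 = 9 comparators per exposed. Assume a known PS with score N(d,1) in the exposed and N(0,1) in comparators; d = 0.5 and 0.8 give c-statistics of 0.64 and 0.71. The weights exp(dx) then leave k/exp(d²) effective comparators per exposed out of k. The model-based variance acts as if there were exactly one. It is therefore too large when k/exp(d²) exceeds 1 and too small when it falls below 1.
- k = 19: 19/1.28 = 14.8 (d = 0.5); 19/9.49 = 2.0 (d = 1.5, c about 0.86). Too wide throughout.
- k = 9: 9/4.22 = 2.1 (d = 1.2, c about 0.80), too wide; 9/9.49 = 0.95 (d = 1.5), slightly too narrow.
- k = 3: 3/4.22 = 0.71 and 3/9.49 = 0.32 at the same two d values, too narrow.

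Simulation (4,000 replicates, three sources pooled, c 0.64–0.71) agrees. At 5% uptake, power is about 65% (63–66% across runs) with model-based intervals, whose coverage exceeds 99%, and 87–90% with the sandwich. At 10% uptake power is about 97% or more either way, but model-based coverage is still about 99%. In four further weighted settings model-based coverage was 98.6–99.5% and sandwich coverage 94.7–95.2%.

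**The case against.** The best reply is that Section 9.7.1 ends with "Further details on the statistical models will be provided in the SAP", and a cluster statement is ordinary SAP content. That reply has force, and it limits the claim. A reader might infer that the protocol declares every record independent in the analysis. It does not; only the study-size simulation does so explicitly. What stands is that the protocol already names the permitted models and allows log-binomial regression for weighted RRs without requiring a variance that is valid there.

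Robust Poisson, the other named model, handles the weights as written and lacks only the cluster term. Weighting is a fallback, so the second part arises only if matching is dropped and log-binomial is chosen with model-based variance.

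Two stronger readings are not supported:
- **Weighting often excludes an RR of 2.5 falsely.** Rates of about 5% and 10% do appear at a true RR of 2.5, but only with 3 comparators per exposed, c-statistics of about 0.80 and 0.86, and no truncation. Truncating at the 99th or 95th percentile cuts them to 3.1% or 2.2% and to 6.0% or 3.1%. With 19 comparators per exposed the rate is 0.1–1.4%. With 9 it is at most about 1.1% up to c 0.80, and 3–4% only at c about 0.86.
- **The interval formally decides the study against 2.5.** That margin appears only in the study-size text. Section 9.7 asks for RRs with 95% intervals and sets no decision rule.

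The ICC and repeat rate are also assumptions. For MCM in Europe, Table 4, footnote 2 closes inclusion in December 2026, under five years after launch, which favours the lower repeat rates.

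**Conclusion.** The point holds at moderate size. The protocol admits repeat pregnancies, treats earlier losses as risk factors, and names RR models with no provision for within-woman correlation. It also leaves open a model whose usual variance is invalid under its own fallback weights.

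For clustering, the upper end of the quoted range needs half of women to contribute two pregnancies in the same arm and an ICC of 0.30. At 10% uptake MCM power stays at about 91% or more even then. At 5% uptake, where stated power is already below 80%, the loss matters more. Pregnancy loss has ample margin, with stated power above 99%.

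For weighting, the main consequence at the planned 5–10% uptake is lost precision rather than false reassurance. Intervals too narrow to be safe arise mainly with few comparators and very poor overlap.

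**What to change.** In Section 9.7.1, require modified Poisson regression (log link) with a sandwich variance clustered on the woman for every crude, matched and weighted RR, in all data sources including those analysed by the data provider. Carry those standard errors into the fixed-effect meta-analysis. In Section 9.5, state that the quoted sample sizes and power assume independent pregnancies. Reporting the number of women beside the number of pregnancies per exposure group, and repeating the primary RRs on each woman's first eligible pregnancy, would show how much the repeats matter.

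The cost is about a sentence in each section and use of a woman identifier in the model. Intervals become slightly wider where women repeat, and the sandwich variance is mildly anti-conservative in sources with very few events. Under very poor overlap its two-sided coverage also falls below 95%, so the planned overlap checks and truncation remain necessary.
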